5.3.5.2 Local tolerability

Local tolerability will be assessed by the investigator according to ‘swelling’, ‘induration’, ‘heat’, ‘redness’, ‘pain’, or other findings’ at the times indicated in the Flow Chart.

5.3.6 Assessment of adverse events

5.3.6.1 Definitions of AEs

Adverse event

An adverse event (AE) is defined as any untoward medical occurrence in a patient or clinical investigation subject administered a medicinal product and which does not necessarily have to have a causal relationship with this treatment.

An AE can therefore be any unfavourable and unintended sign (including an abnormal laboratory finding), symptom, or disease temporally associated with the use of a medicinal product, whether or not considered related to the medicinal product.

Adverse reaction

An adverse reaction is defined as a response to a medicinal product which is noxious and unintended. Response in this context means that a causal relationship between a medicinal product and an adverse event is at least a reasonable possibility. Adverse reactions may arise from use of the product within or outside the terms of the marketing authorisation or from occupational exposure. Conditions of use outside the marketing authorization include off-label use, overdose, misuse, abuse and medication errors.

Serious adverse event

A serious adverse event is defined as any AE which:

- results in death,
- is life-threatening, this refers to an event in which the patient was at risk of death at the time of the event; it does not refer to an event that hypothetically might have caused death if more severe.
- requires inpatient hospitalisation or
- prolongation of existing hospitalisation,

- results in persistent or significant disability or incapacity, or
- is a congenital anomaly / birth defect,
or
- is to be deemed serious for any other reason if it is an important medical event when based upon appropriate medical judgment which may jeopardise the patient and may require medical or surgical intervention to prevent one of the other outcomes listed in the above definitions.

Medical and scientific judgement should be exercised in deciding whether other situations should be considered serious reactions, such as important medical events that might not be immediately life threatening or result in death or hospitalisation but might jeopardise the patient or might require intervention to prevent one of the other outcomes listed above. Examples of such events are intensive treatment in an emergency room or at home for allergic bronchospasm, blood dyscrasias or convulsions that do not result in hospitalisation or development of dependency or abuse. Any suspected transmission via a medicinal product of an infectious agent is also considered a serious adverse reaction.

AEs considered “Always Serious”

Cancers of new histology and exacerbations of existing cancer must be reported as a serious event regardless of the duration between discontinuation of the drug and the occurrence of the cancer.

In accordance with the European Medicines Agency initiative on Important Medical Events, Boehringer Ingelheim has set up a list of further AEs, which by their nature, can always be considered to be “serious” even though they may not have met the criteria of an SAE as given above.

The latest list of “Always Serious AEs” can be found in the Remote Data Capture (RDC) system. A copy of the latest list of “Always Serious AEs” will be provided upon request.

Adverse events of special interest (AESIs)

The term AESI relates to any specific AE that has been identified at the project level as being of particular concern for prospective safety monitoring and safety assessment within this trial, e.g. the potential for AEs based on knowledge from other compounds in the same class. AESI need to be reported to the sponsor’s Pharmacovigilance Department within the same timeframe that applies to SAE, please see above.

The following are considered as AESIs:

Hepatic injury

A hepatic injury is defined by the following alterations of hepatic laboratory parameters:

- an elevation of AST and/or ALT ≥ 3 fold ULN combined with an elevation of total bilirubin ≥ 2 fold ULN measured in the same blood draw sample, and/or
- marked peak aminotransferase (ALT, and/or AST) elevations ≥ 10 fold ULN

These lab findings constitute a hepatic injury alert and the patients showing these lab abnormalities need to be followed up according to the “DILI checklist” provided in the RDC.

In case of clinical symptoms of hepatic injury (icterus, unexplained encephalopathy, unexplained coagulopathy, right upper quadrant abdominal pain, etc.) without lab results (ALT, AST, total bilirubin) available, the Investigator should make sure these parameters are analysed, if necessary in an unscheduled blood test. Should the results meet the criteria of hepatic injury alert, the procedures described in the DILI checklist should be followed.

Intensity of AEs

The intensity grading of AEs will be performed according to RCTC Version 2.0 developed by OMERACT [[R13-3515](#)]. Refer to the ISF for intensity/severity classification. Intensity options are:

Grade 1	mild
Grade 2	moderate
Grade 3	severe
Grade 4	life-threatening

Causal relationship of AEs

The definition of an adverse reaction implies at least a reasonable possibility of a causal relationship between a suspected medicinal product and an adverse event. An adverse reaction, in contrast to an adverse event, is characterised by the fact that a causal relationship between a medicinal product and an occurrence is suspected.

Medical judgment should be used to determine the relationship, considering all relevant factors, including pattern of reaction, temporal relationship, de-challenge or re-challenge, confounding factors such as concomitant medication, concomitant diseases and relevant history.

Arguments that may suggest that there is a reasonable possibility of a causal relationship could be:

- The event is consistent with the known pharmacology of the drug
- The event is known to be caused by or attributed to the drug class.
- A plausible time to onset of the event relative to the time of drug exposure.
- Evidence that the event is reproducible when the drug is re-introduced
- No medically sound alternative aetiologies that could explain the event (e.g. pre-existing or concomitant diseases, or co-medications).
- The event is typically drug-related and infrequent in the general population not exposed to drugs (e.g. Stevens-Johnson syndrome).
- An indication of dose-response (i.e. greater effect size if the dose is increased, smaller effect size if dose is diminished).

Arguments that may suggest that there is no reasonable possibility of a causal relationship could be:

- No plausible time to onset of the event relative to the time of drug exposure is evident (e.g. pre-treatment cases, diagnosis of cancer or chronic disease within days / weeks of drug administration; an allergic reaction weeks after discontinuation of the drug concerned)
- Continuation of the event despite the withdrawal of the medication, taking into account the pharmacological properties of the compound (e.g. after 5 half-lives). Of note, this criterion may not be applicable to events whose time course is prolonged despite removing the original trigger.
- Additional arguments amongst those stated before, like alternative explanation (e.g. situations where other drugs or underlying diseases appear to provide a more likely explanation for the observed event than the drug concerned).
- Disappearance of the event even though the study drug treatment continues or remains unchanged.

5.3.6.2 Adverse event collection and reporting

[figure not shown]
AE Collection

The Investigator shall maintain and keep detailed records of all AEs in their patient files. Records of AEs and AESIs shall include data on the time of onset, end time, and intensity of the event as well as any treatment or action required for the event and its outcome.

The following must be collected and documented on the appropriate CRF(s) by the investigator:

- From signing the informed consent onwards through the residual effect period (REP), until individual patient's end of trial:
 - All AEs (serious and non-serious) and all AESIs.
- After the individual patient's end of trial:
 - The investigator does not need to actively monitor the patient for AEs but should only report relevant SAEs and relevant AESIs of which he may become aware of.

If an individual patient discontinues trial medication prematurely but stays in the trial (i.e. if further visits are planned), the Investigator must report all AEs and all AESIs until the individual patient's end of the trial.

The follow-up period describes the period of time from the last administration of trial medication until the end of trial examination (last per protocol visit).

AE reporting to sponsor and timelines

The Investigator must report SAEs, AESIs, and non-serious AEs which are relevant for the reported SAE or AESI, on the BI SAE form via fax immediately (within 24 hours) to the sponsor's unique entry point (country specific contact details will be provided in the ISF). The same timeline applies if follow-up information becomes available. In specific occasions the Investigator could inform the sponsor upfront via telephone. This does not replace the requirement to complete and fax the BI SAE form.

With receipt of any further information to these events, a follow-up SAE form has to be provided. For follow-up information the same rules and timeline apply as for initial information.

Information required

For each AE, the Investigator should provide the information requested on the appropriate CRF pages and the BI SAE form. The Investigator should determine the causal relationship to the trial medication and any possible interactions between the investigational drug(s) and a Non-Investigational Medicinal Product (NIMP) / Auxiliary Medicinal Product (AMP).

The following should also be recorded as an (S)AE in the CRF and SAE form (if applicable):

- Worsening of the underlying disease or of other pre-existing conditions
- Changes in vital signs, ECG, physical examination and laboratory test results, if they are judged clinically relevant by the Investigator.

If such abnormalities already pre-exist prior trial inclusion they will be considered as baseline conditions.

All (S)AEs, including those persisting after individual patient's end of trial must be followed up until they have resolved, have been sufficiently characterised, or no further information can be obtained.

Pregnancy

In rare cases pregnancy may occur in a clinical trial. Once a patient has been enrolled into this clinical trial and has taken trial medication, the Investigator must report immediately (within 24 hours) a potential drug exposure during pregnancy (DEDP) to the sponsor's unique entry point (country-specific contact details will be provided in the ISF). The Pregnancy Monitoring Form for Clinical Trials (Part A) should be used.

The outcome of the pregnancy associated with the drug exposure during pregnancy must be followed up and reported to the sponsor's unique entry point on the Pregnancy Monitoring Form for Clinical Trials (Part B).

The ISF will contain the Pregnancy Monitoring Form for Clinical Trials (Part A and B).

As pregnancy itself is not to be reported as an AE, in the absence of an accompanying SAE and/or AESI, only the Pregnancy Monitoring Form for Clinical Trials and not the SAE form is to be completed. If there is an SAE and/or AESI associated with the pregnancy an SAE form must be completed in addition.

5.7 APPROPRIATENESS OF MEASUREMENTS

All measurements performed during this trial are standard measurements and are to be performed in order to monitor patients' efficacy, safety and other parameters in an appropriate way. The scheduled measurements will allow monitoring of changes in vital signs, standard laboratory values, and ECG variables that might occur as a result of administration of trial medication. The safety assessments are standard, are accepted for evaluation of safety and tolerability of an intravenously administered drug, and are widely used in clinical trials.

Efficacy and parameters are outlined in [Section 5.1](#)

6.0 INVESTIGATIONAL PLAN

6.1 VISIT SCHEDULE

All patients are to adhere to the visit schedule as specified in the [Flow Chart](#). Investigators are to encourage adherence by the patient to protocol specific activities. Each visit date (with its window) is to be counted from Day 1. The acceptable time windows for follow-up visits and end of trial examination are given in the Flow Chart. All deviations from the planned visit schedule will be documented. If any visit has to be rescheduled, subsequent visits should follow the original visit date schedule. Additional visits for the purpose of re-testing of laboratory parameters or AE monitoring may be included as deemed necessary by the investigator.

If a patient misses an appointment, it will be rescheduled if possible. The relevance of measurements outside the permitted time windows will be assessed no later than at the last Blinded Report Planning Meeting.

Study measurements and assessments are scheduled to occur 'before' trial medication administration at dosing visits and are to be performed and completed prior to the trial drug administration. For planned individual plasma concentration sampling times refer to the Flow Chart. At non-dosing visits sampling should be done after other study procedures have concluded. Sampling times will be recorded and used for determination of pharmacokinetic parameters.

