Main criteria for inclusion:	
 • Male or female patients, aged 18 to 65 years at screening • Diagnosed with Palmoplantar Pustulosis with a minimum ppPASI score of 12 and pppPGA of at least moderate severity 		

Name of company:		Boehringer Ingelheim	
Name of finished product:		Not Applicable	
Name of active ingredient:		BI 655130	
Protocol date: 03 February 2017	Trial number: 1368.15		Revision date: 08 May 2018
	at baseline 
 Patients with associated plaque psoriasis $\geq 10\%$ of the body surface area are excluded 		
Test product	BI 655130		
dose:	900 mg and 300 mg every 4 weeks at Day 1, 29, 57 and 85		
mode of administration:	Intravenous (i.v.)		
Comparator products:	placebo		
dose:	0 mg (placebo) every 4 weeks at Day 1, 29, 57 and 85		
mode of administration:	i.v.		
Duration of treatment:	12 weeks		
Endpoints	Primary Endpoint 
 Efficacy: ppPASI50 at week 16 Safety: Number of patients with drug-related AEs Secondary Endpoint(s) 
 Treatment success defined as achieving a clinical response of 0 or 1=clear/almost clear via PPP Physicians Global Assessment (pppPGA) at week 16 ppPASI75 at week 16 Percent change from baseline in the ppPASI at week 16 		
Safety criteria:	Physical examination, vital signs, 12-lead Electrocardiogram (ECG), laboratory tests, adverse events, serious adverse events and tolerability. The intensity grading of AEs and abnormal laboratory values will be performed according to Rheumatology Common Toxicity Criteria (RCTC) Version 2.0.		
Statistical methods:	Randomisation will be stratified by the presence or absence of plaque psoriasis. For the primary endpoint, the unadjusted risk difference		

Name of company:		Boehringer Ingelheim	
Name of finished product:		Not Applicable	
Name of active ingredient:		BI 655130	
Protocol date: 03 February 2017	Trial number: 1368.15		Revision date: 08 May 2018

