3.3.4.1 Withdrawal from trial treatment

An individual patient is to be withdrawn from trial treatment if:

- The patient wants to withdraw from trial treatment, without the need to justify the decision.
- The patient needs to take concomitant drugs that interfere with the investigational product or other trial medication. Please refer to [Section 4.2.2](#) for restricted medication during this trial.
- The patient can no longer be treated with trial medication for other medical reasons (such as surgery, adverse events, other diseases, or pregnancy).
- The patient has repeatedly shown to be non-compliant with important trial procedures and, in the opinion of both, the investigator and sponsor representative, is not willing or able to stick to the trial requirements in the future.

Given the patient's agreement, the patient will undergo the procedures for the remaining scheduled visits and follow up as outlined in the [Flow Chart](#).

Should the patient not agree to continue the remaining trial visits as scheduled after the premature treatment discontinuation, all efforts should be made to bring the patient to the primary endpoint visit at Week 16 (Day 113, V11), and/or at least to the End of Trial at Week 32 (Day 225, V13).

For all patients the reason for withdrawal from trial treatment (e.g. adverse events) must be recorded in the CRF. These data will be included in the trial database and reported.

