4.2.2.3 Restrictions regarding women of childbearing potential

Women of child bearing potential must maintain an adequate contraception throughout the course of the trial as described in patient information and up to 20 weeks after the last study drug infusion.

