7.3.4 Safety analyses

The safety set, described in [Section 7.3](#), will be used to perform all safety analysis. In general, safety analyses will be descriptive in nature and will be based on BI standards. No hypothesis testing is planned.

Statistical analysis and reporting of adverse events will concentrate on treatment-emergent adverse events. To this end, all adverse events occurring between start of treatment and end of the residual effect period will be considered ‘treatment-emergent’. The REP is defined as 20 weeks after the last dose of trial medication. Adverse events that start before first drug intake and deteriorate under treatment will also be considered as ‘treatment-emergent’. Drug related AEs will be tabulated by system organ class and preferred term after coding according to the current version of the Medical Dictionary for Drug Regulatory Activities (MedDRA).

In addition, the frequency, severity, and causal relationship of adverse events will be tabulated by system organ class and preferred term after coding according to the current version of MedDRA.

Laboratory data will be analysed both quantitatively as well as qualitatively. The latter will be done via comparison of laboratory data to their reference ranges. Values outside the reference range as well as values defined as clinically relevant will be highlighted in the listings. Treatment groups will be compared descriptively with regard to distribution parameters as well as with regard to frequency and percentage of patients with abnormal values or clinically relevant abnormal values.

Vital signs, physical examinations, or other safety-relevant data observed at screening, baseline, during the course of the trial and at the end-of-trial evaluation will be assessed with regard to possible changes compared to findings before start of treatment.

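### Visit windows counted from Day 1 let End of Trial fall up to 10 days before the 20-week residual effect period ends, so active AE collection can stop early

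*Protocol*

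**What the plan says.** Four parts of the protocol bear on how long AEs are observed after the last dose.

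- **Visit timing.** Section 6.1: "Each visit date (with its window) is to be counted from Day 1". It adds: "If any visit has to be rescheduled, subsequent visits should follow the original visit date schedule". The synopsis gives the dosing days as "900 mg and 300 mg every 4 weeks at Day 1, 29, 57 and 85". The Flow Chart puts the last dosing visit (Visit 10) at Day 85±3 and EOT (Visit 13) at Day 225±7. Section 3.3.4.1 confirms the nominal EOT day: "End of Trial at Week 32 (Day 225, V13)".
- **Residual effect period.** Section 7.3.4: "The REP is defined as 20 weeks after the last dose of trial medication". The same section classes AEs from start of treatment to the end of the REP as treatment-emergent and centres the AE analysis on them.
- **AE collection.** Section 5.3.6.2 asks for all AEs over this period: "From signing the informed consent onwards through the residual effect period (REP), until individual patient's end of trial". After that point, "The investigator does not need to actively monitor the patient for AEs but should only report relevant SAEs and relevant AESIs".
- **Completion.** Section 6.2.3 defines trial completion as reaching the Week 32 visit, with no condition on time since the last dose.

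The primary safety endpoint in Section 5.1.1 is the number of patients with drug-related AEs.

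**The concern.** Section 5.3.6.2 names two end points for AE collection, the end of the REP and the individual end of trial, as though they were the same date. One is tied to the last infusion and the other to Day 1. They coincide on the planned days, but each visit has its own window and nothing in the protocol requires EOT to be at least 20 weeks after the dose actually given.

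When EOT comes first, active monitoring stops while the treatment-emergent window of Section 7.3.4 is still open. What is at stake is new-onset, non-serious AEs in the last days of that window. Such an event could count toward the primary safety endpoint if it is judged drug-related and the patient has had no earlier drug-related AE. With 20 patients per arm, one patient moves an arm's rate by 1/20 = 5 percentage points. The protocol's own abbreviation list describes the REP as the time when drug levels or pharmacodynamic effects are still likely, so by its own definition these days matter.

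**Working it through.** **Inputs.** Last infusion: Day 85±3, so Day 82 to 88 (Flow Chart, Visit 10). EOT: Day 225±7, so Day 218 to 232 (Flow Chart, Visit 13). REP: 20 weeks = 20 × 7 = 140 days after the last dose (Section 7.3.4). Both visits are counted from Day 1 (Section 6.1).

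**Formula.** Follow-up = EOT day − last-infusion day. Shortfall = max(0, 140 − follow-up).

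**Planned days.** 225 − 85 = 140 days. This reproduces the 20-week REP exactly, with a shortfall of 0 and no slack.

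**Permitted windows.**

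| Last infusion | EOT | Follow-up (days) | Shortfall (days) |
|---|---|---|---|
| Day 82 | Day 218 | 136 | 4 |
| Day 82 | Day 225 | 143 | 0 |
| Day 82 | Day 232 | 150 | 0 |
| Day 85 | Day 218 | 133 | 7 |
| Day 85 | Day 225 | 140 | 0 |
| Day 85 | Day 232 | 147 | 0 |
| Day 88 | Day 218 | 130 | 10 |
| Day 88 | Day 225 | 137 | 3 |
| Day 88 | Day 232 | 144 | 0 |

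The worst compliant case is 10/140 = 7.1% of the REP. Even the earliest permitted infusion does not protect a patient whose EOT falls on Day 218.

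**How many combinations fall short.** There are 7 infusion days × 15 EOT days = 105 permitted pairs. For infusion on Days 82, 83, …, 88 the number of EOT days giving fewer than 140 days is 4, 5, 6, 7, 8, 9 and 10, which sums to 49. So 49/105 = 47% of pairs fall short, by 210/49 = 4.3 days on average. This is a share of day pairs. It would be a share of patients only if visits were spread evenly over their windows, which the protocol does not say.

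**Who is not affected.** A patient whose last infusion is the third one, given by Day 57 + 3 = Day 60, and who stays to an EOT on Day 218 or later has at least 218 − 60 = 158 days. Early treatment discontinuation with continued visits is therefore covered.

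**The case against.** The strongest reply is that the planned schedule does cover the REP and that what remains is ordinary visit tolerance. The wording in Section 5.3.6.2 can be read as an instruction to collect through the whole REP, and the present window allows a site to comply: a Day 88 infusion reaches 140 days on Day 228, inside the Day 232 limit. Safeguards also exist. Relevant SAEs and AESIs that the investigator learns of after EOT are still reported, AEs persisting at end of trial must be followed up (Section 5.3.6.2), and extra visits for AE monitoring are allowed (Section 6.1). The safety analysis is descriptive, and the windows are the same in all three blinded arms, so they give no reason to expect a difference between arms.

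Most of this stands, and it limits the size of the problem. It does not remove it. The sentence that asks for collection through the REP also ends collection at the individual end of trial, and the visit rules permit the second date to come first.

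A reader might infer more than the documents support:

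- **That much longer gaps are permitted when the last infusion is rescheduled.** Because later visits keep their original dates, a dose after Day 88 would widen the gap day for day. But such a dose is outside the Visit 10 window, and Section 6.1 states no permitted delay, so no size can be attached to it.
- **That pregnancy testing conflicts with the same 20-week period.** Section 4.2.2.3 requires contraception "up to 20 weeks after the last study drug infusion". That is already tied to the last dose, and no test at 20 weeks is required.
- **That the analysis presumes complete observation of the REP.** Section 7.3.4 uses the REP as an upper limit for classing events. It states no person-time or full-observation assumption.

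**Conclusion.** The inconsistency is real and follows from the protocol's own figures without any deviation: a compliant patient can leave active AE collection 130 to 139 days after the last dose, while the treatment-emergent window runs to 140. The maximum loss is 10 days, and it is zero on the planned days. What can be lost is new, non-serious AEs that are not AESIs, starting in that short interval. The effect on the primary safety endpoint is likely to be small, but it cannot be quantified from the protocol, which gives no AE rate for this period and no expected distribution of visit dates. The 7.1% is a share of days, not of events or patients.

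The conclusion assumes that the windows apply as printed in the Flow Chart and that EOT is the individual end of trial for AE collection. It is a modest correction, worth making because it concerns a primary endpoint and costs little.

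**What to change.** Reconcile the Flow Chart and Sections 5.3.6.2, 6.1 and 7.3.4 in two steps.

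1. Keep Visit 13 at Week 32, but add that it takes place no earlier than 140 days after the last infusion actually given. For an in-window last dose the earliest allowed day then runs from 82 + 140 = Day 222 to 88 + 140 = Day 228, all inside the present Day 232 limit. Removing only the early side of the current window is not enough: with EOT on Day 225 or later, still counted from Day 1, a Day 88 infusion leaves 225 − 88 = 137 days, 3 short. The condition has to be tied to the dose.
2. State in Section 5.3.6.2 that all AEs are collected until the later of EOT and the end of the REP, with a telephone AE contact at the end of the REP if EOT has already taken place.

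The cost is that some patients attend EOT a few days later, or receive one call. For patients dosed within the Visit 10 window, the latest permitted EOT day does not move.
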